## 26. Appendix 13: Nyanja - Modified Alcohol Use Disorders Identification Test-Consumption

Kuyesa Kugwiritsa Ntchito Mowa Wosinthidwa (AUDIT-C) (Modified Alcohol Use Disorders Identification Test-Consumption (AUDIT-C))					
GAWO LOYAMBA: kumwa mowa musanalowe					
Mafunso	0 points	1 point	2 points	3 points	4 points
M'miyezi itatu musanalowe m'chipatala, pafupifupi, ni kangati pomwe mumamwa chili conse comwe kuli mowa?	Ayi	Mwezi uliwonse kapena kuchepera	2-4 pa mwezi	2-3 pa sabata	4+ pa sabata
Mwenze kumwa mabotolo angati ya mowa ngati muli pa tsiku lakumwa mowa?	0-2	3-4	5-6	7-9	10 kapena kuposa
Ndi nthawi ziti zimene mumwa zakumwa zofikira mabotolo yali 6 kapena zopitilila pa nthawi imodzi?	Ayi	Pasanathe mwezi uliwonse	Mwezi uliwonse	Mlungu uliwonse	Tsiku lililonse kapena pafupifupi tsiku lililonse
GAWO LACHIWIRI: kumwa mowa mutasiya					
Mafunso	0 points	1 point	2 points	3 points	4 points
Kuyambira kumasulidwa, ni kangati pomwe mumamwa chili conse comwe kuli mowa?	Ayi	Mwezi uliwonse kapena kuchepera	2-4 pa mwezi	2-3 pa sabata	4+ pa sabata
Nthawi yolozera upangiri wogwiritsa ntchito mowa mosayenera: 
 
• Zigoli za 3 kapena kupitilira apo a lowetsedwa kale ndi 2 kapena kupitilira apo atasiya
 
• Zigoli zitatu kapena kupitilira apo mutangotulutsidwa, posatengera kuti munalandira bwanji
 
					

Mawu a M'munsi:

#Ngati munthuyo anena kuti samamwa (mwachitsanzo, kudziletsa), siyani ziwiri zotsatirazi (zidumphani) Zakumwa zokhazikika zitha kuzindikirika motere:

- 1 lager (botolo la 12-ounce, Mosi / Castle, 3% mowa) = 1 unit
- 1 galasi la vinyo (5-ounce, 10% mowa) = 1 unit
- Chidebe chimodzi cha mowa wosawoneka bwino (1-lita, Chibuku Shake Shake, etc., 4% mowa) = mayunitsi 4
- Botolo limodzi la mizimu kuphatikizapo gin, vodka, 'junta', 'twojilijili' (botolo la 200 ml; 40% mowa) = mayunitsi 8
- 1 botolo la Cachasu (200 ml botolo; > 40% mowa) = mayunitsi 10

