**25. Appendix 12: English - Modified Alcohol Use Disorders Identification Test-Consumption**

Modified Alcohol Use Disorders Identification Test-Consumption (AUDIT-C)					
PART ONE: pre-admission alcohol use					
Questions	0 points	1 point	2 points	3 points	4 points
In the 3 months before you were admitted to the hospital, on average, how often did you have a drink containing alcohol?#	Never	Monthly or less	2-4 times a month	2-3 times a week	4+ times a week
When you were drinking alcohol, on average, how many drinks did you have?*	0-2	3-4	5-6	7-9	10 or more
When you were drinking alcohol, on average, how often did you have 6 or more drinks* in one day?	0	Less than monthly	Monthly	Weekly	Daily or almost daily
PART TWO: post-discharge alcohol use					
Questions	0 points	1 point	2 points	3 points	4 points
Since discharge, on average, how often have you had a drink containing alcohol?	Never	Monthly or less	2-4 times a month	2-3 times a week	4+ times a week

When to refer for counseling for unhealthy alcohol use:
 
 
Score of 3 or more pre-admission and 2 or more post-discharge
 
Score of 3 or more post-discharge, regardless of pre-admission score
 
					

Footnotes:

#If the person reports never drinking (i.e., abstinence), leave next two blank (skip them)

\*Standard drink units can be determined as follows:

- 1 **lager** (12-ounce bottle, Mosi/Castle, 3% alcohol) = 1 unit
- 1 glass of **wine** (5-ounce, 10% alcohol) = 1 unit
- 1 container of **opaque beer** (1-liter, Chibuku Shake Shake, etc., 4% alcohol) = 4 units
- 1 bottle of **spirits** including gin, vodka, 'junta', 'twojilijili' (200 ml bottle; 40% alcohol) = 8 units
- 1 bottle of **Cachasú** (200 ml bottle; >40% alcohol) = 10 units

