## 27. Appendix 14: Bemba - Modified Alcohol Use Disorders Identification Test-Consumption

Modified Alcohol Use Disorders Identification Test-Consumption (AUDIT-C)					
PART ONE: pre-admission alcohol use					
Questions	0 points	1 point	2 points	3 points	4 points
Mu myeshi shitatu lintu tabalami teka mu chipatala, miku inga mumona ukuti mwina mwenu alenwo bwalwa?	Never	Monthly or less	2-4 times a month	2-3 times a week	4+ times a week
Umwina mwenu, nga cakuti lelo alenwa, miku inga alenwa ifikali ifya bwalwa?	0-2	3-4	5-6	7-9	10 or more
Miku inga mumwene umwina mwenu alenwa imiku 6 no kuya pantansi mu kulongana kumo kwine?	0	Less than monthly	Monthly	Weekly	Daily or almost daily
PART TWO: post-discharge alcohol use					
Questions	0 points	1 point	2 points	3 points	4 points
Ukufuma epo mwafumine mu chipatala, miku inga mumona ukuti mwina mwenu alenwo bwalwa?	Never	Monthly or less	2-4 times a month	2-3 times a week	4+ times a week

When to refer for counseling for unhealthy alcohol use:
 
 
Score of 3 or more pre-admission and 2 or more post-discharge
 
Score of 3 or more post-discharge, regardless of pre-admission score
 
					

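### The Nyanja AUDIT-C counts bottles where the English form counts standard drinks, and the Bemba items appear to ask about a companion's drinking, yet all three forms share one score and one referral rule

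*Combined protocol and SAP*

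**What the plan says.** Under section 5.1 the CHW screens for unhealthy alcohol use about one month after discharge and refers where feasible. The instrument is in Appendices 12 (English), 13 (Nyanja) and 14 (Bemba). Section 7.1 names these three as the main languages of Lusaka Province.

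All three forms have three pre-admission items (frequency, quantity, heavy-drinking frequency) and one post-discharge item (frequency only, 0 to 4 points). All carry the same referral rule: a pre-admission score of at least 3 with a post-discharge score of at least 2, or a post-discharge score of at least 3 alone.

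- **English.** Item 2 asks "When you were drinking alcohol, on average, how many drinks did you have" and item 3 asks "how often did you have 6 or more drinks* in one day". Both are starred to a table introduced by "Standard drink units can be determined as follows". It counts lager as 1 unit a bottle, opaque beer as 4 a container, cachasu as 10 a bottle, and spirits as "200 ml bottle; 40% alcohol) = 8 units".
- **Nyanja.** Item 2 asks "Mwenze kumwa mabotolo angati ya mowa ngati muli pa tsiku lakumwa mowa". Item 3 asks how often "mumwa zakumwa zofikira mabotolo yali 6 kapena zopitilila pa nthawi imodzi". The bands are the same as in English, and a translated unit table stands below.
- **Bemba.** Item 3 asks "Miku inga mumwene umwina mwenu alenwa imiku 6 no kuya pantansi mu kulongana kumo kwine". The post-discharge item asks "Ukufuma epo mwafumine mu chipatala, miku inga mumona ukuti mwina mwenu alenwo bwalwa".

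The documents describe no back-translation, validation or language adjustment of these forms.

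**The concern.** A common point scale and cut-off make sense only if each form puts the same question. Here the quantity items in Nyanja use a different unit, and the Bemba items seem to have a different subject. A patient's score, and in some cases the referral, could then depend on the language of the interview.

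The score has four uses in the protocol: referral after screening; section 4.4 primary endpoint 7, on seeking services after screening and referral; the exploratory objective on behavioral health prevalence (section 4.3); and the choice of up to 8 extra interviewees, for which section 5.3.2 uses an AUDIT-C cut-off of 3 together with referral.

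**Working it through.** The plan gives no figure to reproduce on this point. The check compares the items and then scores the same drinking both ways with the forms' own points and units.

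**Nyanja: what the items ask.** *Mabotolo* can be read from the document itself. The Nyanja footnote has *botolo* where the English footnote has bottle, for lager, spirits and cachasu. Items 2 and 3 therefore ask for a number of bottles and for six bottles or more.

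**Nyanja: effect on the score.** Pre-admission score = item 1 + item 2 + item 3. Item 2 gives 0, 1, 2, 3 or 4 points for 0-2, 3-4, 5-6, 7-9 or 10 and more. Assumptions: one type of beverage, and the same amount on each occasion. Where each occasion reaches 6, item 3 is scored from the drinking frequency: 1-2 points at monthly or less, 2-3 at 2-4 times a month, 3 at 2-3 times a week.

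| Drinking before admission | In standard units | Literal bottles |
|---|---|---|
| 1 spirits bottle (8 units), monthly or less | 1 + 3 + (1 or 2) = 5-6 | 1 + 0 + 0 = 1 |
| 1 spirits bottle, 2-4 times a month | 2 + 3 + (2 or 3) = 7-8 | 2 + 0 + 0 = 2 |
| 1 cachasu bottle (10 units), 2-4 times a month | 2 + 4 + (2 or 3) = 8-9 | 2 + 0 + 0 = 2 |
| 1 spirits bottle, 2-3 times a week | 3 + 3 + 3 = 9 | 3 + 0 + 0 = 3 |
| 3 spirits bottles (24 units), 2-4 times a month | 2 + 4 + (2 or 3) = 8-9 | 2 + 1 + 0 = 3 |
| 3 lager bottles (3 units), 2-4 times a month | 2 + 1 + 0 = 3 | 2 + 1 + 0 = 3 |

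**Nyanja: effect on referral.** The post-discharge item asks frequency only and is not affected.

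- Post-discharge score 3 or 4: referred on either wording.
- Post-discharge score 0 or 1: not referred on either wording.
- Post-discharge score 2: the decision turns on whether the pre-admission score reaches 3. If pre-admission frequency alone scores 3 or 4, it already does. Only frequency scores of 1 or 2 leave room for a change.

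The first three rows fall in that last group: with a post-discharge score of 2, the patient is referred when scored in units and not when scored in bottles. The fifth row shows that being in the group does not guarantee a change.

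The cut-off of 3 in section 5.3.2 and the prevalence estimate can also shift, to the extent that they use the pre-admission score. The protocol does not say which part of the form they use.

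**Bemba: what the items ask.** All four items contain *mwina mwenu* or *umwina mwenu*, read here as your companion or partner, with a third-person verb (*alenwo*, *alenwa*). Three ask what the patient sees (*mumona*, *mumwene*). The post-discharge item addresses the patient as you for leaving hospital (*mwafumine*) and then puts the drinker in the third person. Item 2 asks *miku inga* (how many times), although its answer bands count drinks.

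**Bemba: effect if that reading is right.** An abstainer whose companion drinks four or more times a week would score 4 after discharge and be referred. A heavy drinker with an abstinent companion would score 0 throughout and not be referred. The post-discharge item alone decides the second branch of the rule and is part of the first, so both branches are affected. No rescoring can recover the patient's own drinking.

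**The case against.** The strongest reply has four parts.

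1. **The Bemba reading rests on translation.** Nothing in the documents glosses *mwina mwenu*. The Bemba PHQ-9 addresses the patient directly, but that does not settle what the phrase means here. The Bemba form also keeps its part headings, answer options and referral rule in English, so a CHW might put the question correctly. This stands, and it is why the Bemba half is conditional. The verb forms still give good reason to check. So does item 10 of the Bemba PHQ-9 (Appendix 10), whose answer options are word for word the Nyanja ones.

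2. **The Nyanja page carries the unit table.** A trained interviewer may convert. This stands as a mitigation, but the items name bottles and nothing on the form asks for conversion. A reader might also treat the missing asterisk as a separate fault. The documents do not support that: other footnote marks are missing from both translated forms, which may be formatting or PDF loss.

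3. **Opaque beer is not called a bottle in Nyanja.** The footnote uses *chidebe* (container). A reader might infer the same reversal as for spirits, but the wording leaves open how such a drinker would answer.

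4. **The reach is limited.** This is a pilot of 100 patients, and alcohol prevalence is exploratory. The synopsis lists three primary endpoints, none of which uses screening; endpoint 7 appears only in section 4.4 and also covers mental health referrals. This stands and lowers the severity.

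**Conclusion.** The concern holds in a limited form, with moderate severity. For Nyanja, the mismatch is shown by the documents themselves. A literal answer takes 5-6 points off the pre-admission score for one spirits bottle 2-4 times a month (7-8 against 2) and nothing for lager. This assumes that the interviewer does not convert.

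A reader might infer that language decides referral for Nyanja speakers in general. It does not: the decision can change only with a post-discharge score of exactly 2 and a pre-admission frequency score of 1 or 2.

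For Bemba, a reader might conclude that the form certainly records someone else's drinking. The documents make this likely on their grammar but do not prove it. If it is confirmed, the Bemba fault is the more serious of the two.

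A reader might also see a threat to the trial's main effectiveness result. Being alive and virally suppressed at 6 months (section 5.2.4) makes no use of AUDIT-C.

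The overall bias cannot be sized, because the documents give no mix of languages or beverages. Language choice is stated for consent (section 9.5); its use for screening is inferred from the existence of the three forms.

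**What to change.** - Have Appendices 13 and 14 independently back-translated against Appendix 12.
- Reword Nyanja items 2 and 3 to ask for standard drinks, with an explicit pointer to the unit table. Alternatively, record container type and number and convert with the form's own table, which would also settle opaque beer.
- Reword the four Bemba items to the second person, with item 2 asking for the number of drinks.
- Leave the referral rule unchanged; the point concerns only whether the three forms feed it the same quantity.
- If the forms are already in use, record the interview language and report alcohol results by language. Do not pool Bemba scores from the old form if back-translation confirms the fault.

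The cost is a revised translation of two one-page forms and a protocol modification through the review described in section 9.2. No patients, visits or procedures are added. The cost of waiting is greater: Nyanja answers recorded only as bottle bands cannot be fully converted afterwards, and Bemba answers, if the fault is confirmed, cannot be recovered at all.

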## 27. Appendix 14: Bemba - Modified Alcohol Use Disorders Identification Test-Consumption

Modified Alcohol Use Disorders Identification Test-Consumption (AUDIT-C)					
PART ONE: pre-admission alcohol use					
Questions	0 points	1 point	2 points	3 points	4 points
Mu myeshi shitatu lintu tabalami teka mu chipatala, miku inga mumona ukuti mwina mwenu alenwo bwalwa?	Never	Monthly or less	2-4 times a month	2-3 times a week	4+ times a week
Umwina mwenu, nga cakuti lelo alenwa, miku inga alenwa ifikali ifya bwalwa?	0-2	3-4	5-6	7-9	10 or more
Miku inga mumwene umwina mwenu alenwa imiku 6 no kuya pantansi mu kulongana kumo kwine?	0	Less than monthly	Monthly	Weekly	Daily or almost daily
PART TWO: post-discharge alcohol use					
Questions	0 points	1 point	2 points	3 points	4 points
Ukufuma epo mwafumine mu chipatala, miku inga mumona ukuti mwina mwenu alenwo bwalwa?	Never	Monthly or less	2-4 times a month	2-3 times a week	4+ times a week

When to refer for counseling for unhealthy alcohol use:
 
 
Score of 3 or more pre-admission and 2 or more post-discharge
 
Score of 3 or more post-discharge, regardless of pre-admission score
 
					

### Footnotes:

#If the person reports never drinking (i.e., abstinence), leave next two blank (skip them)

\*Standard drink units can be determined as follows:

- 1 **lager** (12-ounce bottle, Mosi/Castle, 3% alcohol) = 1 unit
- 1 glass of **wine** (5-ounce, 10% alcohol) = 1 unit
- 1 container of **opaque beer** (1-liter, Chibuku Shake Shake, etc., 4% alcohol) = 4 units
- 1 bottle of **spirits** including gin, vodka, 'junta', 'twojilijili' (200 ml bottle; 40% alcohol) = 8 units
- 1 bottle of **Cachasú** (200 ml bottle; >40% alcohol) = 10 units

